8.2 Missing, Unknown, or Partial Dates

Start Date		Stop Date						Missing/ Ongoing	
		Complete: yyyymmdd		Partial: yyyyymm		Partial: yyyy			
		<1 st dose	≥1 st dose	<1 st dose yyyymm	≥1 st dose yyyymm	<1 st dose yyyy	≥1 st dose yyyy		
Partial: yyyymm	= 1 st dose yyyymm	2	1	n/a	1	n/a	1	1	
	≠ 1 st dose yyyymm		2	2	2	2	2	2	
Partial: yyyy	= 1 st dose yyyy	3	1	3	1	n/a	1	1	
	≠ 1 st dose yyyy		3		3	3	3	3	
Missing		4	1	4	1	4	1	1	

1 = Impute as the date of first dose

2 = Impute as the first of the month

3 = Impute as January 1 of the year

4 = Impute as January 1 of the stop year

Note: If the start date imputation leads to a start date that is after the stop date, then there is a data error and the start date is not imputed.

Imputation rules for partial or missing stop dates:

1. Initial imputation
 - a. For partial stop date "mmyyyy", impute the last of the month.
 - b. For partial stop date "yyyy", impute December 31 of the year.
 - c. For completely missing stop date, do not impute.
2. If the stop date imputation leads to a stop date that is after the death date, then impute the stop date as the death date.
3. If the stop date imputation leads to a stop date that is before the start date, then there is a data error and the stop date is not imputed.

Imputation rules for partial or missing death dates:

1. If death year and month are available but day is missing:
 - a. If "mmyyyy" for last contact date = "mmyyyy" for death date, set death date to the day after the last contact date.
 - b. If "mmyyyy" for last contact date < "mmyyyy" for death date, set death date to the first day of the death month.
 - c. If "mmyyyy" for last contact date > "mmyyyy" for death date, data error and do not impute.

Sponsor: Bristol-Myers Squibb

Protocol no: MB130-068

If both month and day are missing for death date or a death date is totally missing, set death date to the day after the last contact date.

8.3 Visit Windows

Visit windows as defined in the protocol are closely monitored by clinical monitors. A protocol deviation will be documented if assessments were recorded outside the visit windows, but the assessment is recorded in the clinical database at the planned visit. For longitudinal summaries of data, assessment recorded at the planned visits in the clinical database are included and displayed in tables with visit based structure.

If there are multiple records within the same visit window, then the value in the visit window closest to the day of the planned visit is selected.

8.4 Treatment-Emergent Adverse Events

Treatment-emergent adverse events (TEAEs) are those that first occur or increase in severity or relationship to study treatment after the first dose of study treatment and not more than 30 days after the last dose of study treatment. All AEs that change in severity or relationship to study treatment are assigned a new start date and captured as a new record.

The definitions of AE and SAE can be found in the [Protocol Appendix 8](#). If an AE causality or severity, seriousness or relationship to IP is missing, they will not be imputed.

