4.3.1 Adverse Events

- Incidence and frequency of treatment-emergent adverse events (AEs) and serious adverse events (SAEs).

The definition of AEs and SAEs as well as their time periods for collection can be found in the Protocol Section 8.5.3.1 and Protocol Appendix 8.

Adverse events of special interest (AESI) will include following AEs:

1. Injection site reactions (injection-site erythema and edema)
2. Gastrointestinal events (Diarrhea, frequent bowel movements, nausea, vomiting, abdominal pain)
3. Bone-related events (Osteoporosis, osteopenia, bone and joint injuries, fractures (except tooth fracture), endocrine abnormalities of gonadal function not elsewhere classified (NEC), hyperparathyroid disorders, hypoparathyroid disorders, parathyroid disorders NEC, parathyroid analyses, metabolic bone disorders, vitamin D abnormal, vitamin D decreased, vitamin D deficiency, and miscellaneous events related to bone density)

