6.2 Safety Analyses

6.2.1 Adverse Events

All adverse events will be presented based on the safety population by treatment group, and pooled BMS-986036.

A summary of treatment-emergent AEs, including the number of events reported and the number and percentage of participants reporting

- at least one AE
- any severe AE
- any treatment-related AE
- any AEs of special interest
- any severe treatment-related AE
- any AE with outcome of death

Sponsor: Bristol-Myers Squibb

Protocol no: MB130-068

- any serious AE
- any treatment-related SAE
- any AE leading to the discontinuation of study treatment
- any treatment-related AE leading to the discontinuation of study treatment
- any AE leading to discontinuation of the study
- any treatment-related AE leading to discontinuation of the study

A breakdown of the number and percentage of participants reporting each AE, categorized by system organ class (SOC) and preferred term (PT) will be presented. Maximum severity will be summarized for all TEAE by SOC and PT. Counts for AEs will be by participant not event and participants are only counted once within each SOC or PT.

Only treatment-emergent AEs will be summarized in tables. All AEs will be included in listings. In addition DILI will be presented graphically.

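### An adverse event that worsens on treatment is counted more than once in the planned event total, because its split records are not linked

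*SAP*

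**What the plan says.** **Record rule (SAP 8.4).** Adverse events whose severity or causality assessment changes "are assigned a new start date and captured as a new record". The trigger is a change in either direction, so improvement also opens a record.

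**Treatment-emergent definition (SAP 8.4).** Treatment-emergent events are "those that first occur or increase in severity or relationship to study treatment after the first dose of study treatment". The window closes 30 days after the final dose. A decrease is not named.

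**Planned output (SAP 6.2.1).** The overview of treatment-emergent events is described as "including the number of events reported and the number and percentage of participants reporting" each of a list of event types. Tables are restricted to treatment-emergent events; listings show everything. For the breakdown by system organ class (SOC) and preferred term (PT), the rule is "Counts for AEs will be by participant not event and participants are only counted once within each SOC or PT". Severity is tabulated at its maximum.

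**Related text.** The safety endpoint in SAP 4.3.1 and protocol 9.4.2 names both incidence and frequency. Protocol 9.5.3 treats an event as treatment-emergent simply if it occurs after the first dose. Protocol Appendix 8 defines an adverse event as a new occurrence or a worsening, and has an SAE report updated when its intensity or relationship changes.

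Neither document states how the records of one episode are joined, or how distinct episodes are counted. Table shells are kept in a separate document (SAP Appendix 2).

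**The concern.** An event count is useful only if one clinical episode contributes one event. Here the database unit is a stretch of constant severity and constant causality opinion, and the overview counts events without going back to the episode. A patient with one bout of diarrhoea that goes from mild to moderate supplies two events. So does a patient whose mild event is first judged unrelated and later judged related, with no clinical change at all.

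This programme does use event-level figures in its risk narrative: protocol 6.3.2.1 compares 55 gastrointestinal events on active drug with 14 on placebo in the Phase 2a studies and reports mean durations per event. A similar summary built from split records would show more events, each apparently shorter. SAE totals could also differ between the safety reports, which are updated, and the analysis database, where a change opens a new record.

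**Working it through.** There is no stated figure to reproduce. The check is to apply the SAP's rules to example episodes in one participant, all within the treatment-emergent window unless noted.

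Records per episode = 1 + number of changes in severity or relationship.

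Two readings of the treatment-emergent flag are possible:
- *SAP 8.4 reading*: a record counts if it is a first occurrence or an increase.
- *Start-date reading*: a record counts if its own start date is after the first dose, as protocol 9.5.3 would allow.

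| Course of one episode | Records | Events, SAP 8.4 reading | Events, start-date reading | Participants |
|---|---|---|---|---|
| Mild throughout | 1 | 1 | 1 | 1 |
| Mild, then moderate | 2 | 2 | 2 | 1 |
| Mild and unrelated, then mild and related | 2 | 2 | 2 | 1 |
| Moderate, then mild | 2 | 1 | 2 | 1 |
| Mild, then moderate, then mild | 3 | 2 | 3 | 1 |
| Moderate before first dose, mild after it | 2 | 0 | 1 | 0 or 1 |

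On either reading, an on-treatment episode that worsens or has its relationship upgraded is counted at least twice. Records opened by a decrease matter only on the start-date reading.

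**Size on the SAP 8.4 reading.** Let *p* be the share of events with an upward change and *u* the number of upward changes in each of those. Then

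inflation factor = 1 + *p* × *u*.

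The documents give neither quantity. Assuming *u* = 1:
- *p* = 0.10: 1 + 0.10 × 1 = 1.10
- *p* = 0.30: 1 + 0.30 × 1 = 1.30

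So 100 true episodes would be tabulated as 110 to 130 events.

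**Which outputs are touched.** Participant counts and percentages, SOC/PT tables and maximum-severity tables take each participant once, so extra records of an on-treatment episode do not change them. Only the number of events in the overview moves.

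**The case against.** The best defence is that the SAP already filters. Its definition admits only first occurrences and increases, and tables show only treatment-emergent events, so a record opened by an improvement should never reach the count. That stands as a reading of SAP 8.4, and it means the mild-moderate-mild course is two tabulated events, not three. It does not help with the upward change, which the definition expressly admits as a further event. Nor does the SAP say whether the flag is set by comparison with the preceding record or from the new start date, and protocol 9.5.3 is worded more loosely.

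A second defence is the sentence about counting by participant, not event. It belongs to the SOC/PT breakdown and cannot govern an overview that asks for events and participants side by side.

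Third, no planned test uses event counts, the word frequency in the endpoint is not defined as number of events (SAP 6.1.1 uses frequency counts for participants), and the unseen shells may define the count. All of this is fair and limits the importance of the point. The counting rule still belongs in the SAP.

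A reader might also infer that the inflation favours one arm, because mild gastrointestinal events on active drug took a mean of 6 weeks to resolve (protocol 6.3.2.1) and visits are 4 weeks apart. The documents do not support this. No placebo duration is given, no re-grading is reported, 8 of the 10 moderate events resolved within a mean of 8.7 days, and visits are 8 weeks apart after Week 24.

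**Conclusion.** The point holds, and it is minor. As written, the event total in the SAP 6.2.1 overview counts an on-treatment episode more than once if it worsens or its relationship is upgraded. If 10-30% of events have one such change, the total is about 10-30% too high. That range is an assumption, since the documents contain no re-grading data.

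A reader might go further, count every change in either direction, and reach 1 + 0.30 × 2 = 1.60 for events that go up and then down. That figure requires improvement records to be flagged as treatment-emergent, contrary to the SAP 8.4 definition, so it is not the size to quote. It would also be wrong to say that the total measures re-grading and not events: within the assumed range, most counted records are still distinct episodes. No direction of bias between arms can be claimed.

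**What to change.** Add to SAP 8.4 and 6.2.1:

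> Treatment emergence is determined for each record first, by comparison with the preceding record of the same episode; a record created only by a decrease in severity or relationship is not a new TEAE. For the number of events, records of the same preferred term in the same participant, where one starts on the stop date of the previous record or the next day, are linked as one episode and counted once, at the maximum treatment-emergent severity and strongest relationship, with onset at the first treatment-emergent record. Listings remain at record level.

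The order matters. If records were linked first and given the earliest start date, an occurrence that began before dosing and worsened on treatment would acquire a pre-dose onset and could lose its treatment-emergent status. Under this wording it counts once, from the worsening.

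The cost is a few lines of SAP text and a short derivation, with no new data. The one drawback is a small risk of merging two separate episodes of the same term that happen to run back to back.

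### Adverse events with missing severity or relationship cannot count as severe or treatment-related, so those per-arm rates are unflagged lower bounds

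*SAP*

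**What the plan says.** SAP 8.4 sets the rule: "If an AE causality or severity, seriousness or relationship to IP is missing, they will not be imputed".

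SAP 6.2.1 sets the tables that use these attributes. On the population: "All adverse events will be presented based on the safety population by treatment group, and pooled BMS-986036". On the counting unit: "Counts for AEs will be by participant not event and participants are only counted once within each SOC or PT". The overview has 12 rows. Six of them need a recorded severity or relationship:

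- severe;
- treatment-related ("any treatment-related AE");
- severe and treatment-related;
- treatment-related SAE;
- treatment-related event leading to discontinuation of study treatment;
- treatment-related event leading to discontinuation of the study.

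A seventh row, "any serious AE", needs recorded seriousness. The section adds: "Maximum severity will be summarized for all TEAE by SOC and PT". It also says: "All AEs will be included in listings".

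Neither document gives a worst-case rule, a category for missing values or a sensitivity analysis for these fields.

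**The concern.** An event with a blank severity does not meet the condition for the severe row, and one with a blank relationship does not meet the condition for the related rows. In the table, a participant whose only candidate event is blank looks the same as one who had no such event. The percentage is then a minimum, but a reader would take it as the observed rate.

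These rows matter. The safety objective (Protocol 7.3, SAP 3.3) is to demonstrate safety, and Protocol 6.2.1 says that Phase 3 design and dose selection will draw on this study's safety results. With about 49 participants per arm, one or two are visible in a percentage.

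The SAP takes the cautious side on some neighbouring questions. Several patterns of missing or partial start date in SAP 8.2 follow "1 = Impute as the date of first dose", which tends to make an event treatment-emergent. The table does not name the record type; I take it to cover adverse events.

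**Working it through.** The plan states no figure for this point, so there is none to reproduce. The check covers direction and possible size.

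**Inputs**
- Rule for blanks: not imputed (SAP 8.4).
- Denominator: safety population of the arm, counted by participant (SAP 6.2.1).
- Arm size: about 49, from 197 randomized to four arms (Protocol 6.2). Pooled drug group: 3 × 49 = 147.
- m, the number of participants in an arm whose only candidate event for a row has the attribute blank: not given. I assume a range of 0 to 5.

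**Direction within one arm.** Let T be the number of participants who truly had a severe event, and O the number with at least one event recorded as severe. Everyone counted in O is also in T, so O ≤ T. With n fixed, O/n ≤ T/n. Equality holds when every participant with a blank severe event also has another event recorded as severe. The same argument applies to relationship.

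A simulation agrees. It used 5,000 arms of 49, Poisson event counts with mean 2, a severe probability between 0 and 0.3, and a missing probability between 0 and 0.2. The observed count exceeded the true count in 0 arms, was lower in 2,674 and was equal in 2,326.

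**Size.** The largest shortfall in a row is m/n.

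| m | Arm of 49 | Pooled drug, 147 |
|---|---|---|
| 0 | 0 | 0 |
| 1 | 2.0 points | 0.7 points |
| 2 | 4.1 points | 1.4 points |
| 3 | 6.1 points | 2.0 points |
| 5 | 10.2 points | 3.4 points |

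Illustration with assumed counts: 5 participants have a recorded severe event, and 2 more have only an event of unknown severity. The plan reports 5/49 = 10.2%. Counting the unknowns as severe gives 7/49 = 14.3%. The true value lies between the two.

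**Difference between arms.** Suppose both unknowns are truly severe. If both are in a drug arm, drug minus placebo is understated by 2/49 = 4.1 points. If both are on placebo, it is overstated by 4.1 points. If there are two in each arm, the difference is unchanged.

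**Dependence on the denominator.** SAP 6.5 words its general denominator for percentages loosely. If participants with unknown values were dropped, the example becomes 5/47 = 10.6%, and in the same simulation the rate was above the true rate in 3,455 of 5,000 arms. SAP 6.2.1 does not ask for this, so I use the safety population throughout.

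**The case against.** **Blanks should be rare.** Protocol Appendix 8 has a physician determine intensity and the causality of all adverse events. Protocol Appendix 1 allows blank eCRF fields only where the completion guidelines permit, and requires investigator review and signature. This stands, and it limits the point to a minor one.

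**The tables may show missing values anyway.** SAP 8.4 forbids imputation but does not forbid a missing row, and the table shells are in a separate document (SAP Appendix 2). This stands as a possibility. It would help the maximum-severity table, but the yes/no overview rows would still need a rule.

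**Little is lost from view.** A treatment-emergent event with a blank still counts in the at-least-one-AE row, the special-interest row, the death row, both any-cause discontinuation rows and the SOC/PT counts. It also appears in the listings. This stands.

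**The proposed rule replaces a lower bound with an upper bound.** That is true. The benefit is that the choice is cautious and the number affected is visible.

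Four stronger readings are tempting, and the documents do not support them:

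- *The rule favours the drug.* It applies equally to placebo, and investigators assess events under the blind (Protocol 8.4.4.1). Only the per-arm direction is certain.
- *Rates can never be too high.* That is true of this rule alone. Protocol 8.5.3.1 collects SAEs from consent, so an SAE with a partial start date could be moved to first dose under SAP 8.2 and be counted as treatment-emergent.
- *The rule is the opposite of the SAP's other missing-data rules.* Fully missing stop dates (SAP 8.2) and non-biopsy endpoints (SAP 6.4) are not imputed either.
- *The 29 May 2020 cut-off makes blanks likely.* Neither document says that attributes are less complete for recent events. SAP 7.3 plans a later analysis once all data through Week 52 are collected.

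**Conclusion.** The point holds for severity and relationship, as a minor reporting gap. For the rows in SAP 6.2.1 that need those fields, each arm's percentage is a lower bound that the plan does not label as one. The shortfall is at most 2.0 points per affected participant in an arm of 49, and 0.7 points in the pooled drug group. At an assumed 0 to 2 affected participants per arm, it is 0 to 4.1 points.

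This rests on a safety-population denominator and on blank values not meeting a row's condition. The frequency is unknown, and zero is possible.

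A reader might extend the point to a rule that missing seriousness should count as serious. The arithmetic has the same direction, but the documents do not support the remedy. SAEs have their own eCRF pages (Protocol 8.5.3.1) and must be reported within 24 hours (Protocol Appendix 8). A blank there should be rare and is a matter for a query. Recoding it would tabulate an SAE that was never reported as one.

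**What to change.** In SAP 8.4, replace the sentence on missing attributes with wording such as:

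> In summary tables, a TEAE with missing relationship is counted as related and a TEAE with missing severity is counted as severe. Listings show the value as missing. A footnote gives the number of such events by treatment group. Missing seriousness is resolved by query before database lock; any remaining blank is reported as missing and is not reclassified as an SAE.

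The cost is one SAP edit, a programming default and a footnote. No new data are needed. The downside is that related and severe rates may be slightly over-counted. The footnote makes the extent visible and lets a reader recover the lower bound from the listings.

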8.5 Adverse Events of Special Interest

The sponsor has developed a list of AEs of Special Interest for the BMS-986036 program based on the known biologic class effects, the mechanism of action, and clinical study data. These will include the following:

- Injection site reactions
- Gastrointestinal events (Diarrhea, frequent bowel movements, nausea, vomiting, abdominal pain)
- Bone-related events (Osteoporosis, osteopenia, bone and joint injuries, fractures (except tooth fracture), endocrine abnormalities of gonadal function not elsewhere classified (NEC), hyperparathyroid disorders, hypoparathyroid disorders, parathyroid disorders NEC, parathyroid analyses, metabolic bone disorders, vitamin D abnormal, vitamin D decreased, vitamin D deficiency, and miscellaneous events related to bone density)

8.6 Liver Biopsy Scoring

Histological assessment of the liver tissue sample will be conducted by a blinded Central Pathologist. The central reader will be a medical doctor, board certified in pathology, with experience in liver pathology in a clinical study setting. Additional details on the acquisition, quality requirements, histological preparation, and shipping of histological samples are in the Central Laboratory Manual and the Central Pathology Manual or Charter.

Histological Scoring

NASH CRN

For associated primary and secondary endpoints, the NASH CRN system will be used to score the histologic samples and results are reported as the NAFLD Activity Score (NAS) and the NASH CRN Fibrosis Score. The NASH CRN system is based on the concept that necroinflammatory lesions and stage of fibrosis should be evaluated separately; it assesses liver biopsies for degree of steatosis (0-3), lobular inflammation (0-3), hepatocellular ballooning (0-2), and fibrosis (0-4).

Sponsor: Bristol-Myers Squibb

Protocol no: MB130-068

NAS

The 3 categories of steatosis, lobular inflammation, and ballooning scores are added together in an unweighted fashion to determine the NAS, which ranges from 0 to 8 (see table below).

Histology Variable	Grade	Score
Steatosis	< 5%	0
	5%-33%	1
	> 33% - 66%	2
	> 66%	3
Lobular Inflammation ^a	none	0
	< 2	1
	2 - 4	2
	> 4	3
Ballooning	none	0
	few	1
	many	2

NAS = NAFLD Activity Score

^a Foci per x200 field

Fibrosis

NASH CRN Fibrosis

Fibrosis is staged separately from NAS on a 0-4 scale: 0 (none); 1 (perisinusoidal or periportal fibrosis); 2 (perisinusoidal and portal/periportal fibrosis); 3 (bridging fibrosis); 4 (cirrhosis).

Participants will be evaluated for progression to cirrhosis (NASH CRN Fibrosis stage 3 to stage 4) at Week 24.

Ishak

A modified Ishak scoring system will also be used to stage fibrosis in the histologic samples. The Ishak system (0-6 scale) was originally developed to grade portal-based liver fibrosis associated with viral hepatitis. The modified Ishak system has been adapted to stage central-based liver fibrosis associated with NASH, and it also uses a 0-6 scale:

- 0: No fibrosis
- 1: centrilobular pericellular fibrosis
- 2: centrilobular and periportal fibrosis
- 3: bridging fibrosis (few bridges)
- 4: bridging fibrosis (many bridges)
- 5: early or incomplete cirrhosis
- 6: established or advanced cirrhosis

Sponsor: Bristol-Myers Squibb

Protocol no: MB130-068

